- Adherence to current guidelines on the management of acute pulmonary embolism released by the European Society of Cardiology concerning diagnosis, risk stratification, hospitalization and treatment. These items will be evaluated in the overall study population and compared between patients admitted in every-day clinical practice in Cardiology, Emergency or Internal Medicine Departments.

Primary study outcome

The co-primary study outcomes are

- in-hospital death and
- death at 30 days from the diagnosis of pulmonary embolism.

Secondary study outcomes

The secondary study outcome are:

- death or clinical deterioration at 30 days from the diagnosis of pulmonary embolism.
- pulmonary embolism-related death or clinical deterioration at 30 days from the diagnosis of pulmonary embolism
- Adherence to current guidelines on the management of acute pulmonary embolism released by the European Society of Cardiology regarding diagnosis, risk stratification and treatment.

For all patients, the cause of death will be reported as assessed by the attending physician and classified as:

- Unexpected
- Pulmonary-embolism related
- Due to bleeding
- Due to cardiovascular events other than pulmonary embolism
- Due to cancer
- Other non-cardiovascular causes

Pulmonary embolism-related death is defined as i) death where pulmonary embolism is the most probable cause or ii) based on objective diagnostic testing performed before death or iii) as assessed at autopsy (autopsy is not mandatory).

Documentation on study outcome events (in-hospital and 30 day deaths) will be centrally collected in order to allow an independent adjudication committee to definitely adjudicate the cause of death.

Clinical deterioration is defined as the occurrence of at least 1 of the following (25):

- (iv) the need for cardiopulmonary resuscitation;
- (v) systolic blood pressure <90 mm Hg for at least 15 minutes, or drop of systolic blood pressure by at least 40 mm Hg for at least 15 minutes, with signs of end-organ hypoperfusion (cold extremities, or urinary output <30 mL/h, or mental confusion);
- (vi) the need for catecholamine infusion (except for dopamine at a rate of <math><5 \mu\text{g kg}^{-1} \text{min}^{-1}</math>) to maintain adequate organ perfusion and a systolic blood pressure of >90 mm Hg.

Adherence to ESC guidelines 2014 will be assessed concerning:

- diagnosis
- risk stratification
- treatment

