- any bleeding compromising hemodynamics;
- spontaneous hematoma larger than 25 cm², or 100 cm² if there was a traumatic cause;
- intramuscular hematoma documented by ultrasonography;
- epistaxis or gingival bleeding requiring tamponade or other medical intervention or bleeding from venipuncture for >5 minutes;
- hematuria that was macroscopic and was spontaneous or lasted for more than 24 hours after invasive procedures;
- hemoptysis, hematemesis or spontaneous rectal bleeding requiring endoscopy or other medical intervention;
- or any other bleeding considered to have clinical consequences for a patient such as medical intervention, the need for unscheduled contact (visit or telephone call) with a physician, or temporary cessation of a study drug, or associated with pain or impairment of activities of daily life.

STUDY PROCEDURES

Patient information and informed consent

Before being admitted to the study, the subject must consent to participate after full information about the nature, scope, and possible consequences of the study.

The documents must be in a language understandable to the subject and must specify who informed the subject. A copy of the signed informed consent document must be given to the subject. The original signed consent document will be retained by the investigator.

Moreover, a letter will be provided to every patient to inform his/her primary physician about the subject's participation in the study - provided the subject agrees to the primary physician being informed.

After reading the informed consent document, the subject must give consent in writing.

No personal patient's contact details (like mobile phone number) will be recorded in the study database.

Visits schedule and follow-up

Patients will be evaluated at the time of diagnosis of pulmonary embolism (baseline), at discharge (FU 1) and at 30 days (± 4) from index pulmonary embolism (FU 2).

For some patients, discharge may occur beyond 30 days from index pulmonary embolism. These patients will have two study assessments only (baseline and 30 days).

At baseline, patient status at presentation (hemodynamics, respiratory failure, etc.), the relevant patient history (including concomitant medications), diagnostic strategies and assessments for risk stratification will be recorded.

Telephone call is allowed for the 30-day follow-up using standardized interview (Appendix 1).

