Data from routine patient data collection points or telephone interviews at the respective site should be documented directly in the Medical Records and entered shortly thereafter into the eCRF.

Early Study Termination

In case a patient terminates the study early, reason for early study termination (lost to follow-up, investigator's decision, adverse events, withdrawal of consent etc.) will be recorded.

The treating physician should at least get awareness of the patient's vital status at the time of the early termination of patient participation in the study.

Withdrawal of Consent

In accordance with the Declaration of Helsinki and other applicable regulations, a patient has the right to withdraw consent for participation in the study at any time and for any reason without prejudice to his or her future medical care by the physician or at the institution.

If a patient withdraws consent to participate in the study, the investigator will complete and report the observations as thoroughly as possible up to the date of consent withdrawal and including the date of the final contact with the patient. The investigator will clearly document the reason (if given) for consent withdrawal in the medical record and will complete the associated electronic case report form (eCRF) section.

Data Management

An electronic CRF system will be used for data capture.

A data management plan will be created in the study start phase and will describe all functions, processes, and specifications for data collection, cleaning and validation. The eCRFs will include automated plausibility checks (e.g. range checks, conditional checks, etc.) at data entry to obtain immediate feedback if data are missing, out of range, illogical or potentially erroneous and allow for correction or confirmation by the site. Concurrent manual data review will be performed based on parameters defined in the data management plan. If necessary, queries will be manually generated within the eCRF system and followed up for resolution.

Critical fields will be defined that need to be filled in by the site prior to signing the eCRF.

Data Entry/Electronic Data Capture

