expecting an incidence of death of 3% and 0.5% for patients with intermediate or low-risk, respectively, it is estimated that 2100 patients with intermediate pulmonary embolism and 2500 with low-risk pulmonary embolism should be included in the study. In the same time frame, it is estimated that around 400 patients with high-risk pulmonary embolism will be observed. The expected mortality in these patients is 10-15%. According to these estimates, we would be able to have about 100 deaths in study patients and this will empower assessment of independent predictors of death. Besides already known predictors (hypotension, right ventricle dysfunction – imaging and BNP – and increased troponin), the role of comorbidities and clinical features as well as adherence to current guidelines on pulmonary embolism (risk stratification adequate, appropriateness of acute treatment) as determinants of prognosis will be assessed. The same features will be tested as predictors of death or clinical deterioration.

The inclusion of patients in each risk category (low, intermediate and high risk for death) will be stopped when the predicted number of patients is complete. An alert signal will appear in the e-CRF once the estimated sample is completed.

Planned analyses

The following analyses are planned:

1. Final analysis on the data
2. Three data snapshots of the study data are planned and will be analysed before the final analysis will take place after data base lock:
 1. Snapshot: Q4 2018
 2. Snapshot: Q3 2019
 3. Snapshot: Q1 2020

All analyses will contain a summary of all data plus a summary of data per patient groups.

The writing of the SAP for the study will start immediately after the finalisation of the observational plan and a version 1.0 of the SAP will be available before the start of the study. If the SAP needs to be revised for a snapshot or the final analysis, the adaptation will always be finalised and signed before the extraction of data for the respective snapshot or the final data base lock, respectively.

Statistical methodology

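### After early termination the protocol asks only for vital status on that day, so day-30 death, a co-primary outcome, need not be known for these patients

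*Protocol*

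**What the plan says.** The protocol's Primary study outcome section names two co-primary outcomes, in-hospital death and "death at 30 days from the diagnosis of pulmonary embolism". The Primary Objectives section makes the predictors of each a co-primary objective.

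The Early Study Termination section says that the reason for leaving is to be documented, with these examples: "lost to follow-up, investigator's decision, adverse events, withdrawal of consent etc.) will be recorded". On outcome data it says that the treating physician "should at least get awareness of the patient's vital status at the time of the early termination". The minimum asked for is thus "vital status at the time of the early termination of patient participation in the study", with no mention of day 30. For withdrawn consent, the next section has the investigator report observations "as thoroughly as possible up to the date of consent withdrawal and including the date of the final contact with the patient".

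For patients who remain in the study, day-30 status comes from the third visit, and the Visits schedule and follow-up section adds: "Telephone call is allowed for the 30-day follow-up using standardized interview". That section gives clinical records and telephone interviews as the data sources. Central collection of documents on deaths (Secondary study outcomes; Quality Control) serves to adjudicate the cause of deaths that have been reported.

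**The concern.** The minimum is set at the wrong time point. A patient known to be alive on leaving at day 8, say, may be dead or alive at day 30, and the outcome is defined at day 30. The study is non-interventional, so no study treatment is stopped when a patient leaves. An adverse event or an investigator's decision therefore gives no reason in itself to stop finding out whether the patient died.

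The planned 30-day death rate with its 95% confidence interval and the logistic models both need a known day-30 status. Kaplan-Meier and Cox analyses can censor at last contact, but they assume that censoring is unrelated to the risk of death. If it is related, the rate is biased. Odds ratios and hazard ratios can be biased too, in particular where the link between loss and death differs by predictor or by department. An analysis plan can choose how to treat missing status, but it cannot recover status that was never sought.

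**Working it through.** **The protocol's own expected deaths.** The Sample Size section has "expecting an incidence of death of 3% and 0.5% for patients with intermediate or low-risk, respectively", with 2100 and 2500 patients in these classes, and about 400 high-risk patients with 10-15% mortality.

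- Intermediate: 2100 × 0.03 = 63
- Low: 2500 × 0.005 = 12.5
- High: 400 × 0.10 to 0.15 = 40 to 60
- Total: 115.5 to 135.5 deaths among 5000, or 2.31% to 2.71%

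The protocol states about 100 deaths. That difference is a separate matter. The relative bias below does not depend on the total.

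**Model for missing status.** Let *p* be the true 30-day death rate, *m* the fraction leaving early with unknown day-30 status, and *r* their risk of death relative to the other patients. The rate among patients with known status is

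*q* = *p* / (1 − *m* + *m r*),

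the relative bias is 1/(1 − *m* + *m r*) − 1, and the number of hidden deaths is 5000 × (*p* − (1 − *m*) *q*).

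The protocol gives neither *m* nor *r*, so both are assumptions. With *p* = 115.5/5000 = 2.31%:

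| *m* | Patients | *r* | *q* | Hidden deaths | Relative bias |
|---|---|---|---|---|---|
| 2% | 100 | 1 | 2.31% | 2.3 | 0 |
| 5% | 250 | 1 | 2.31% | 5.8 | 0 |
| 1% | 50 | 3 | 2.26% | 3.4 | −2.0% |
| 2% | 100 | 3 | 2.22% | 6.7 | −3.8% |
| 5% | 250 | 3 | 2.10% | 15.8 | −9.1% |
| 5% | 250 | 5 | 1.92% | 24.1 | −16.7% |

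Worked case: *m* = 2%, *r* = 3 gives *q* = 0.0231/1.04 = 0.0222. Known deaths are 4900 × 0.02221 = 108.8, so 115.5 − 108.8 = 6.7 are hidden.

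**Comparison with sampling error.** The 95% half-width is 1.96 × √(0.0231 × 0.9769/5000) = 0.42 percentage points. The shift is 0.09 points for *m* = 2%, *r* = 3, and about 0.39 points (2.31 − 1.925) for *m* = 5%, *r* = 5.

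**Limits without any assumption on risk.** Suppose 2% have unknown status and the rate is 2.31% among the other 4900 (113.2 deaths). The overall rate then lies between 113.2/5000 = 2.26% if all 100 are alive and 213.2/5000 = 4.26% if all are dead.

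**The case against.** The strongest reply is that the wording sets a floor. Sites may collect more, the 30-day visit form includes dead/alive status, and clinical records are a permitted source, so deaths at the treating hospital can be found without contacting the patient. This stands. A reader might infer that day-30 death will be unknown for everyone who leaves early, but the text supports only that it is not required to be known.

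A reader might also take the list of reasons as telling sites to stop observation after an adverse event. It does not: these are categories to be recorded, and the protocol does not say how often they would be used.

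Nor do the documents say that patients with unknown status will be counted as survivors. How such patients are analysed is a matter for the SAP, which was not available for this check.

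On size, the reply is that nothing in the protocol shows loss to be frequent or linked to death, and that moderate scenarios shift the rate by far less than its confidence half-width. Both points are fair. It is tempting to give the early leavers the 10-15% mortality of the high-risk class. With 1% leaving at 10% mortality that would hide 5/115.5 = 4.3% of deaths, and with 5% leaving at 15% mortality 37.5/135.5 = 27.7%. The documents give no ground for borrowing that risk, and hidden deaths are not the same as bias in the rate.

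The reply does not explain why the stated minimum falls on a day other than the one on which the outcome is defined.

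**Conclusion.** The point holds as a poorly set data-collection rule. For early terminations, the required minimum does not determine a co-primary outcome, and later analysis cannot repair that.

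The size is conditional. It is zero if those who leave have the same risk as the rest, apart from the loss of some events. The rate is about 4% too low in relative terms if 2% leave at three times the risk, and about 17% too low if 5% leave at five times the risk. These fractions and risk ratios are assumptions. The claim that the 30-day rate will be biased downward, stated as a fact, goes beyond the documents.

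The point still merits a change because events are few. At 2% early termination, the 100 patients with unknown status would be nearly as many as all expected deaths. In the low-risk class, with 12.5 deaths expected, three hidden deaths would be 3/12.5 = 24%.

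Ending data collection when consent to it is withdrawn is proper and is not part of the defect.

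**What to change.** Replace the sentence on vital status in Early Study Termination with a rule to this effect: for every early termination other than withdrawal of consent to further data collection, the site seeks vital status at day 30 and, where the patient has died, the date of death, from clinical records or the telephone contact to which the patient agreed. Add that an adverse event or an investigator's decision does not by itself end ascertainment of vital status.

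Both routes are already in the protocol (Visits schedule and follow-up; Patient Information, Informed Consent). The letter for the primary physician should not be used as a third route. It depends on the patient's agreement and only informs about participation, so using it would add a data source and a change to the consent form.

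The cost is a change to one paragraph and a few record checks or calls. Under the assumed 2% to 5%, that is 100 to 250 patients over about 200 centres, or 0.5 to 1.25 per centre. The handling of patients whose status stays unknown can be left to the SAP.

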- global management (the composite of diagnosis, risk stratification and treatment)

Six process indicators were selected, based on recommendations from ESC guidelines (6). The indicators are:

- (1) Time from diagnosis to initiation of anticoagulant treatment. The time of CT angiography or of lower limbs ultrasonography will be considered as time of diagnosis.
- (2) Number of diagnostic tests applied and their order within the diagnostic work-up based on estimated pre-test probability of pulmonary embolism.
- (3) Type, number and timing (within 24 hours) of tests performed for prognostic assessment.
- (4) Use of systemic thrombolysis or percutaneous manoeuvre associated with intravenous heparin for at least 48 hours in hemodynamically unstable patients.
- (5) home treatment or short hospital stay (<48 hours) in patients with low-risk pulmonary embolism
- (6) The number, dose and sequence of antithrombotic agents according to currently validated regimens.

Safety Objective

The safety objective of this study is to collect and evaluate real-world safety data on bleeding events in patients with acute pulmonary embolism.

Safety Outcomes

The primary safety outcome is:

- Major bleeding according to ISTH definition, occurring up to 30 days from the diagnosis of index pulmonary embolism.

Major bleeding, defined (as per ISTH guidelines), as acute clinically overt bleeding (i.e. bleeding that is visualized by examination or radiologic imaging) associated with one or more of the following:

- decrease in hemoglobin of 2 g/dl (1.2 mmol/L) or more;
- transfusion of 2 or more units of packed red blood cells;
- bleeding that occurs in at least one critical site [intracranial, intra-spinal, intraocular (within the corpus of the eye; thus, a conjunctival bleed is not an intraocular bleed), pericardial, intra-articular, intramuscular with compartment syndrome, or retroperitoneal];
- bleeding that is fatal;
- bleeding that necessitates acute surgical intervention

Major bleeding events will also be further sub-classified as life-threatening or non-life threatening. A life-threatening major bleed is defined as a bleeding event that is either intracranial or is associated with haemodynamic compromise requiring intervention.

The secondary safety outcome is:

- Clinically relevant non-major bleeding.

Clinically relevant non-major bleeding event defined as acute clinically overt bleeding that does not meet the criteria for major and consists of:

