For all secondary endpoints, summary statistics, frequencies and rates (including the 95% confidence interval) will be presented overall and within the different patients' groups (see 9.3.1 for details). Kaplan-Meier estimates will be calculated for the occurrence of death or clinical deterioration at 30 days from diagnosis of pulmonary embolism and of pulmonary embolism-related death or clinical deterioration at 30 days from diagnosis of pulmonary embolism.

In analogy to the primary endpoint, comparisons of patients will be performed for the following subgroups

- patients admitted in every-day clinical practice in Cardiology, Emergency or Internal Medicine Departments
- patients at low, intermediate or high risk for death according to ESC guidelines definition.

For all secondary endpoints results of the Cox proportional hazard regression models will be evaluated as well (hazard ratios and corresponding 95% confidence intervals). If relevant differences in baseline characteristics are detected, these variables will be added to the model as additional covariates. Further data like patient characteristics or laboratory data will be summarized as appropriate, i.e. by means of absolute numbers and percentages or by means of standard statistics.

Furthermore, it will be looked at safety endpoints

- major bleedings
- clinically relevant non-major bleedings .

Definition of adherence

Firstly, the number of indicators that each patient will have met will be counted and divided by the total number for which the patient was eligible, obtaining the proportion of adherence.

The adherence score is defined as the ratio of the diagnostic tests/prognostic evaluations/treatment actually prescribed to those that should theoretically have been prescribed. Adherence will be calculated separately for each step (diagnosis/prognostic stratification/treatment) and globally for the overall patient's management. The theoretical diagnostic/prognostic/treatment/global scores will be calculated for every patient, taking into account diagnostic/prognostic/treatment eligibility criteria, guideline-based contraindications to tests/drugs or treatments.

We define as adherent to the care pathway a patient with a proportion of met indicators equal or greater than 80%. Sensitivity analyses will be performed at different cut-offs, and considering adherence

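### Adherence on hospitalization is an objective for all patients but is scored only at low risk, so a stable patient with right ventricle dysfunction treated at home can count as 100% adherent

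*Protocol*

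**What the plan says.** Protocol, Secondary Objectives, asks for adherence to the ESC guidelines "concerning diagnosis, risk stratification, hospitalization and treatment". It adds: "These items will be evaluated in the overall study population and compared between patients admitted" to the three types of department. The study aim lists the same four domains, and so does the secondary outcome in the Synopsis. The secondary outcome in the body of the protocol (Secondary study outcomes) leaves hospitalization out.

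The same section lists six process indicators. The only one on place of care is indicator (5): "home treatment or short hospital stay (<48 hours) in patients with low-risk pulmonary embolism". Indicator (4) is limited to haemodynamically unstable patients. Indicators (1), (2), (3) and (6) carry no risk restriction.

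Under Definition of adherence, the indicators met are "counted and divided by the total number for which the patient was eligible, obtaining the proportion of adherence". An adherent patient is one with "a proportion of met indicators equal or greater than 80" per cent. The section continues: "Adherence will be calculated separately for each step (diagnosis/prognostic stratification/treatment) and globally" for overall management. The points rules that follow concern tests and treatment regimens only. "Sensitivity analyses will be performed at different cut-offs, and considering adherence" as an ordinal and a continuous variable.

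The guideline summary in Rationale and Background says that stable patients with right ventricle dysfunction or injury should be admitted, and labels them intermediate risk.

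**The concern.** Hospitalization is one of four named adherence domains, to be evaluated in everyone, but it has a scoring rule in one risk class only. The score can penalise keeping a low-risk patient too long. It cannot penalise failing to admit a stable patient with right ventricle dysfunction.

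This matters in two places. The hospitalization objective has no defined measure for intermediate-risk or high-risk patients. The adherence score is also the exposure in the planned analysis of the causal effect of guideline-adherent care on survival, so a place-of-care decision against the protocol's own guideline summary would enter that analysis as full adherence. The planned sensitivity analyses do not expose it, because a score of 100% passes every cut-off and remains 100% as a continuous variable.

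**Working it through.** **Inputs.** The six indicators are in Secondary study outcomes. The denominator rule and the 80% cut-off are in Definition of adherence. The planned numbers are in Sample Size: 2100 intermediate-risk, 2500 low-risk and 400 high-risk patients, 5000 in all. The protocol states no figure of its own on this point, so there is none to reproduce.

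**Eligible indicators by risk class**

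| Class | Indicators | Number eligible |
|---|---|---|
| Low | 1, 2, 3, 5, 6 | 5 |
| Intermediate (stable, right ventricle dysfunction or injury) | 1, 2, 3, 6 | 4 |
| High (unstable) | 1, 2, 3, 4, 6 | 5 |

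**Score = met / eligible**

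- Intermediate risk, treated at home, all four met: 4/4 = 100%.
- Intermediate risk, admitted, all four met: 4/4 = 100%. The two decisions cannot be told apart.
- Low risk, kept 48 hours or longer, all else met: 4/5 = 80%. This passes the main cut-off and fails any higher one.

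**Step scores.** Points are given for diagnosis, risk stratification and treatment. A patient treated at home who has full points on each is at the good level on all three steps. The protocol gives no formula for the global score, but nothing that enters it reflects place of care.

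**Would adding an admission indicator to the main score help?** The intermediate-risk denominator would go from 4 to 5.

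- Treated at home, all else met: 4/5 = 80%, still adherent under the retained rule.
- Admitted, one miss elsewhere: 3/4 = 75% (not adherent) now, and 4/5 = 80% (adherent) after the change.

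So the binary classification would not remove the patient of interest, and it would admit others who have a real miss in diagnosis, stratification or treatment.

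**Possible size.** The frequency is not given. Assuming 1% to 5% of 2100: 0.01 × 2100 = 21 and 0.05 × 2100 = 105. As a share of all patients: 21/5000 = 0.4% and 105/5000 = 2.1%. At the protocol's 3% mortality for intermediate risk: 0.03 × 21 = 0.6 and 0.03 × 105 = 3.2 deaths, against the protocol's expectation of about 100.

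**The case against.** The strongest reply is that the indicators are a chosen set and need not cover every recommendation. The secondary outcome in the body of the protocol names three domains, and the composite and the points rules match it. On that view the fault is a wording mismatch between objective and outcome. This stands in part: the formula is consistent with that version of the outcome. It does not remove the study aim, the objective or the Synopsis outcome, all of which name hospitalization.

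Second, the study enrols patients admitted to departments, so home treatment at intermediate risk should be uncommon. This stands and limits the size. It does not exclude the case: indicator (5) and note (g) to the study schedule both provide for home-treated patients.

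Third, place of care is recorded and can be tabulated by risk class. This also stands. A reader might infer that hospitalization cannot be evaluated at all, and the protocol does not support that. What is missing is a scoring rule.

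Fourth, a reader might also count an intermediate-risk patient discharged within 48 hours as a breach. The protocol does not support this. Its guideline summary sets no minimum stay for these patients, and it equates a stay under 48 hours with out-patient management only when describing a trial in low-risk patients. Scoring patients on not being discharged alive within 48 hours would also make every early in-hospital death concordant, which builds the outcome into the exposure.

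Fifth, the thresholds for meeting indicators (1), (2), (3) and (6) are not in the protocol and may properly be left to the SAP. The 4/4 is therefore conditional on those four being met. The indicator list and the eligible-only denominator are fixed in the protocol.

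**Conclusion.** The point holds as a gap between a stated objective and its scoring. Adherence on hospitalization is to be evaluated in all patients but is scored only at low risk. A stable patient with right ventricle dysfunction or injury who is treated at home can score 100%, contrary to the protocol's own guideline summary. The arithmetic needs only the indicator list and the denominator rule, with the other four indicators taken as met.

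The effect is probably small. The 21 to 105 patients rest on an assumed 1% to 5% that has no basis in the protocol. They also treat all 2100 intermediate-risk patients as having documented right ventricle dysfunction or injury, which is an upper bound.

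Two stronger conclusions are not supported. The direction of any bias in the adherence-survival analysis cannot be derived from the protocol. Nor does the gap show that the 80% rule or the six indicators should be changed for the main analysis. This is an inexpensive improvement worth making, not a flaw that undermines the study.

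**What to change.** Keep the six indicators and the 80% rule as they are for the main analysis, and add two things.

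1. **A separate hospitalization adherence item, reported by risk class.**
   - Low risk: score as indicator (5) does now.
   - Intermediate risk with documented right ventricle dysfunction or injury, and high risk: concordant if hospitalized, discordant if treated at home. Define this by the initial place-of-care decision, not by length of stay or survival to 48 hours, so that early death does not determine the exposure.
   - Report the number of patients in whom right ventricle status was not assessed.
2. **One sensitivity analysis of adherence and survival** that classes home treatment of such intermediate-risk or high-risk patients as not adherent, whatever their proportion of met indicators.

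The cost is a short scoring rule, some programming and one more sensitivity analysis. Home treatment or hospitalization is already in the study schedule, so no new data are needed. Few patients are likely to be reclassified, so the sensitivity analysis may differ little from the main one. The item would still give the hospitalization objective a measure in every risk class.
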